### Participants

All patients signed consent prior to enrolling in the study. We recruited patients referred to an outpatient vestibular rehabilitation clinic with chief complaints of dizziness and/or imbalance. The participants first underwent an initial vestibular physical therapy evaluation of approximately 60 minutes. The evaluation included: detailed history, oculomotor screening which included saccades, smooth pursuit and convergence, assessment of spontaneous and gaze evoked nystagmus with and without infrared goggles, Dix-Hallpike and roll test to rule out benign paroxysmal positional vertigo (BPPV), and bedside head impulse test to screen for vestibulo-ocular (VOR) impairment. The assessment also included gait speed and gait stability with head turns in both horizontal planes and vertical planes, as well as the modified clinical test of sensory integration to assess static balance. Peripheral vestibular hypofunction was diagnosed by either positive findings on bithermal caloric testing during videonystagmography and/or positive bedside head impulse test, head shaking nystagmus and gaze evoked nystagmus and/or clinical history characterized by sudden onset of vertigo lasting hours, aural symptoms unilaterally and ruling out other central causes. Central vestibular conditions were diagnosed based upon history of head injury leading to symptoms, history of resected acoustic neuroma or migraine history with episodic vertigo. We excluded patients if they had bilateral or unstable vestibular loss or another neurological condition, active BPPV, acute orthopedic injuries, peripheral neuropathy and visual impairment not corrected with glasses.

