### Procedure

When a clinician identified a patient as eligible, they reviewed the informed consent and explained the study procedures. Following consent, patients underwent a baseline assessment including functional measures (Functional Gait Assessment [FGA], Timed-Up and Go [TUG], The Four-Square Step Test [FSST]), and self-reported questionnaires (Visual Vertigo Analog Scale [VVAS][27–29], Activities Specific Balance Confidence Scale [ABC], The Dizziness Handicap Inventory [DHI]). The assessment also included a postural control test using HMD. Standing hips-width apart on the floor, participants experienced two levels of visual surround and white noise while their head sway was recorded via the HTC Vive Pro headset. The total duration of the session was approximately 45 minutes. After the baseline assessment, the patients were randomized to 8 sessions of either traditional vestibular rehabilitation or C.S.I training followed by an immediate post assessment.

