**NCT04268745**

**ANALYSIS PLAN**

**May 6th, 2021**

The **specific aims** of this pilot project are:

**Aim #1:** Determine the extent to which sensory integration strategies differ between individuals with unilateral vestibular hypofunction and age-matched peers. Participants' head sway will be recorded as they experience two levels of moving stars and white noise, while standing on the floor or a compliant surface. Our working hypothesis is that patients with vestibular hypofunction utilize substitution strategies such that they will demonstrate greater visual and auditory reliance compared with controls, particularly when somatosensory cues are reduced via the support surface. We will then explore whether these mechanism changes after training.

**Aim #2:** Develop the protocol and establish the feasibility of a randomized controlled trial (RCT) comparing C.S.I. training to standard vestibular rehabilitation. Following the assessment, the patients will be randomized into standard vestibular rehabilitation vs. C.S.I. training. This pilot study will enable us to test the feasibility of our recruitment, randomization procedures, establish attrition rate, and test the training protocol.

**Aim #3:** Generate pilot data for sample size calculation for a properly powered RCT. The follow up RCT will test the effect of C.S.I. training on: Visual Vertigo Analog Scale (VVAS), Functional Gait Analysis (primary); balance confidence, overall disability (descriptive). In our preliminary study, 8 patients met the inclusion criteria for the current proposal. Following the C.S.I. training, they had a large effect size of 1.17 on the VVAS. The current study will allow us to identify the between-group effect size for the VVAS and for a functional gait outcome.

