#### **Data Analysis:**

**Aim 1:** For each of the measures of interest we will fit a linear mixed effects model to compare the age-matched controls to patients with vestibular hypofunction while accounting for the inherent multi-level study design (person, conditions, repetitions). The models will include main effects of group, visual condition, auditory condition, surface condition, as well as their interactions, while adjusting for age. *P*-values for the fixed effects will be calculated through the Satterthwaite approximation for the degrees of freedom for the T-distribution. We will repeat the analysis following the intervention, adjusting for group assignment and pre-intervention values. ABC and DHI will be used to describe the sample.

**Aim 2:** No statistical analysis needed.

**Aim 3:** First, following the intent-to-treat principle, a linear regression model will be fit with the VVAS and FGA as the primary dependent variable, on treatment group, controlling for baseline covariates (age and other self-reported questionnaire measures) to improve the precision of the treatment effect estimate, as well as pre-test scores. The potential efficacy of the intervention will be assessed based on a significant coefficient for treatment status. Second, as described above, we will fit a pattern mixture model to multiply impute any missing values, and use Rubin's rules to pool coefficients and their standard errors from the regression models fit to each imputed dataset. Data generated from this pilot randomized trial will be used to calculate the sample size needed for future, adequately powered, randomized controlled trials by estimating the difference in means for the treatment groups (i.e. a future expected effect size) as well as the variance of the primary outcomes and the values of other parameters necessary to compute the power function.

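### Does the SAP leave open whether central vestibular patients count as hypofunction patients in the Aim 1 comparison with controls?

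*Protocol*

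**What the plan says.** In the SAP, Aim #1 is to "Determine the extent to which sensory integration strategies differ between individuals with unilateral vestibular hypofunction and age-matched peers". The Data Analysis section for Aim 1 fits a linear mixed model to "compare the age-matched controls to patients with vestibular hypofunction", with group, visual, auditory and surface conditions, their interactions, and age. It has no term for type of diagnosis. After treatment, "We will repeat the analysis following the intervention, adjusting for group assignment and pre-intervention values".

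The protocol's Participants section recruits on symptoms at a vestibular rehabilitation clinic. It sets out how peripheral hypofunction was diagnosed and follows this with: "Central vestibular conditions were diagnosed based upon history of head injury leading to symptoms, history of resected acoustic neuroma or migraine history with episodic vertigo". The exclusions begin: "We excluded patients if they had bilateral or unstable vestibular loss or another neurological condition, active BPPV". Central vestibular conditions are not listed by name.

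The same patients appear to serve Aim 1 and the trial. The protocol's Procedure section, after describing the head-sway test, says: "After the baseline assessment, the patients were randomized to 8 sessions of either traditional vestibular rehabilitation or C.S.I training". SAP Aim #2 agrees: "Following the assessment, the patients will be randomized into standard vestibular rehabilitation vs. C.S.I. training".

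**The concern.** Aim 1 is about hypofunction, yet the protocol describes two diagnostic classes and does not plainly shut the second one out. If central patients are enrolled, have the sway test and are randomized, an analyst could take all enrolled patients as the patient group. The reported contrast would then describe a mixture under the name of hypofunction. Alternatively, the analyst could leave central patients out. With no sentence on the point, that choice might be made after the data are seen.

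What would be at stake is the Aim 1 hypothesis that patients with hypofunction rely more on vision and sound than controls do. A lesser worry concerns Aim 3: the effect size and variance passed to the follow-up trial would belong to a mixed population without the SAP saying so.

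**Working it through.** The documents give no figure for Aim 1 to reproduce: no sample size, power, standard deviation or case mix. The main check is therefore of the text.

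**Step 1: are central patients enrolled?** This is an inference.

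- For: the central criteria stand in the Participants section beside the peripheral ones, and the exclusions do not name them.
- Against: other neurological disease is excluded, and the central sentence can be read as describing how referred patients were sorted at evaluation.

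The first reading is the more natural, but neither document states it. If central patients were not enrolled, there is no conflict.

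**Step 2: if they are enrolled, whom does the plan put in the Aim 1 group?**

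| Element | Source | Effect on the group |
|---|---|---|
| Patients with vestibular hypofunction | SAP, Data Analysis, Aim 1 | Limits the contrast to hypofunction |
| Unilateral | SAP, Aim #1 | Limits it to one-sided loss |
| Diagnostic criteria for peripheral hypofunction | Protocol, Participants | Say who qualifies |
| Bilateral loss excluded | Protocol, Participants | Leaves unilateral cases, so the shorter wording in Data Analysis loses nothing |

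Taken literally, these give patients who meet the peripheral definition, on one side. That is the restriction an explicit rule would impose. A restricted group also needs no diagnosis term in the model, so the absence of one is not a gap.

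**Step 3: what if someone pooled anyway?** Let *f* be the central share of patients, and *k* the central patients' excess reliance over controls divided by that of peripheral patients. Both are assumptions. The pooled contrast as a fraction of the peripheral contrast is (1 − *f*) + *f* × *k*. At *f* = 0.30:

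- *k* = 0: 0.70 + 0 = 0.70
- *k* = 0.5: 0.70 + 0.15 = 0.85
- *k* = 1: 0.70 + 0.30 = 1.00
- *k* = 1.5: 0.70 + 0.45 = 1.15

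Nothing in the documents caps *k* at 1, so pooling could shrink the contrast, leave it alone or inflate it.

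Restricting also has a cost. With equal numbers of controls and enrolled patients, equal variances, and a simple comparison of two means in place of the mixed model, the standard error relative to the pooled one is √[(1 + 1/(1 − *f*))/2]. At *f* = 0.30 this is √[(1 + 1.4286)/2] = √1.2143 = 1.10, about 10% wider. These figures only illustrate; they are not evidence about this trial.

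**Step 4: Aim 3.** The regressions of the Visual Vertigo Analog Scale and the Functional Gait Assessment on treatment follow intention to treat, and the SAP does not limit them to hypofunction. The estimate applies to whoever was randomized. Saying so, or tabulating diagnoses by arm, changes no result. A diagnosis covariate would join age, questionnaire scores and pre-test scores in a pilot-sized model, with no demonstrated gain.

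**The case for a change.** The strongest contrary argument is that the two diagnostic classes can overlap, so the word hypofunction does not settle every case. A patient with a resected acoustic neuroma is central by history but might also have a positive caloric or head-impulse result. The peripheral definition asks for other central causes to be ruled out, but that phrase may belong only to the clinical-history route. How to class such a patient is not written down, and an unwritten choice can be made late. A sentence fixing it would cost almost nothing, since diagnosis comes from the screening evaluation and no new data are needed.

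The overlap is real, and the protocol could be plainer on central enrolment. But the issue is then confined to patients who meet both definitions, a subset of the central share. For central patients who do not meet the peripheral definition, the SAP's wording already decides the matter. The two readings are not equally open, because pooling needs the analyst to set aside the group that the SAP names.

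The link from the Participants section to Aim 1 is also looser than it first appears. The protocol text describes the rehabilitation trial, mentions no age-matched controls, and has the sway test done on the floor only, whereas SAP Aim #1 adds a compliant surface. It is therefore not shown to be the full eligibility text for Aim 1. This weakens the link without breaking it, because the SAP itself ties the Aim 1 patients to randomization.

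**Conclusion.** The concern does not call for a change. The ambiguity about central enrolment is genuine, but the plan followed as written leads to the restricted contrast that an added rule would specify. What is missing is a clarifying detail, chiefly how to class a patient who meets both definitions, and analysts can be expected to settle it sensibly and report it.

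No size can be attached to the effect. The documents give neither the central share nor the direction of any difference; the range of 0.70 to 1.15 at an assumed 30% central applies only if the analyst departs from the SAP's named group. The conclusion rests on reading the SAP's Aim 1 wording literally and taking the protocol's peripheral definition, with bilateral loss excluded, as its meaning. This is a pilot, and neither the randomized comparison nor the analysis of its two primary outcomes depends on the point.

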### Procedure

When a clinician identified a patient as eligible, they reviewed the informed consent and explained the study procedures. Following consent, patients underwent a baseline assessment including functional measures (Functional Gait Assessment [FGA], Timed-Up and Go [TUG], The Four-Square Step Test [FSST]), and self-reported questionnaires (Visual Vertigo Analog Scale [VVAS][27–29], Activities Specific Balance Confidence Scale [ABC], The Dizziness Handicap Inventory [DHI]). The assessment also included a postural control test using HMD. Standing hips-width apart on the floor, participants experienced two levels of visual surround and white noise while their head sway was recorded via the HTC Vive Pro headset. The total duration of the session was approximately 45 minutes. After the baseline assessment, the patients were randomized to 8 sessions of either traditional vestibular rehabilitation or C.S.I training followed by an immediate post assessment.

### System

Our platform runs at 120 frames per second with either HTC Vive or Oculus Rift, on a Windows 10 laptop with 8GB RAM, Intel i7-7820HK CPU, Nvidia GTX 1080 Max-Q GPU, and Bose SoundTrue around-ear headphones II. The software was developed in C# with Unity3D 2018.2.0f1(64-bit) (Unity Technologies, San Francisco, California). The system utilizes SteamVR. Oculus Rift and HTC Vive both operate at 90 Hz refresh rate, 110 degrees field of view, and a high-definition video of 1080x1200 resolution for each eye. The graphics of the subway station, airport terminal building, and subway trains are modeled in Maya and imported to Unity3D. The rest of the 3D objects are modeled in Unity3D. The subway station model and airport model replicate a real subway station in New York City and a real airport terminal in the US. The contents in the system are fully controllable by the user interface (see Figure 3). Three-dimensional sounds were implemented using Wwise middleware and Google Resonance audio plugin. Using the head-tracking data, audio is modulated according to the position of the listener's head. The technology allows for creation of a rich soundscape in all directions around the listener. Audio assets used in the system are divided into two main groups: sound objects and ambiances. Sound objects are attached to the visual objects in the scene and their position is changing accordingly. Sounds include: footsteps, trains, announcements, cars, balls, airplanes, etc. Ambiances are created from original recordings from different locations in New York. These include different background sounds, i.e. sounds of the crowd chatter, distant trains, wind, birds, traffic, and general room tone of each of the spaces. All of the sounds used in the system are assigned to three different intensity levels which relate to the increasing complexity of the soundscape.

***Randomization and Group Allocation:*** We used a blocked randomization method. Instead of randomizing each patient individually, this scheme randomizes several patients at a time in such a way as to ensure that equal numbers are allocated to each group across each segment of time during the length of the study. For example, if the block size is four, we randomize four patients at a time ensuring that two patients are allocated to the C.S.I group and two patients to the traditional group. As it happens, there are six different possible ways we could randomize four patients equally to two treatments. The randomization was done following the baseline assessment and only the study statistician had access to the randomization sequence.

### **Interventions**

Following the baseline assessments, we randomized patients to a C.S.I. group or a traditional vestibular rehabilitation control group. We planned each program to be 8 weeks (1 30-minute weekly session + home program). We conducted a post-assessment, identical to the baseline assessment, within one week from the completion of the 8th intervention session.

The main difference between participants was the timing of progression which was individualized based on patient symptoms (dizziness and / or instability). Each exercise (in clinic or home) was prescribed at the highest level of challenge that was considered safe (i.e., no loss of balance or no significant increase in dizziness). We assigned all patients a home exercise program (the C.S.I group had similar exercises without eyes closed tasks, effectively 2 minutes less exercise per day) which they were asked to complete twice daily, for 5 to 10 minutes. Their home program consisted of gait, gaze stability, and static balance activities.

For patients in the C.S.I. group the progression of environments started with the most salient to the patient and this varied from patient to patient and eventually most patients completed several different environments (e.g., street, subway, airport). The duration varied with starting point at 1 minute with increase in time up to 5 minutes based upon patients' symptoms. Beyond duration, the exact progression the patient underwent varied by therapist. Some therapists chose to change the complexity of the scene (i.e., increased amount people, increased speed of people adding sounds, or changing directions of walking), while others chose to add tasks in the scene (i.e., walking for a maximum of 4-5 steps, changing base of support or adding head turns).

The following are the exercise variation for the traditional group: **Gait:** walking with head turns, progress with range, speed and planes of head movement; change of walking base of support: wide, normal, tandem; **Gaze:** focus on a target while moving head side to side / up down. Progress with speed, duration, busier background, standing to walking; **Balance:** standing balance tasks, progress with BOS (wide to narrow to tandem), support surface, eyes closed, duration, head turns. See Table 1 for further details.

**Table 1.** A detailed description of the study's intervention programs

	Experimental Group	Control Group
Study Initiation	Eligible participants will be provided with patient education and a basic home exercise program (gait, balance, no exercises with eyes closed) while they are considering participation in the study.	
Program Dose	8 weeks, 1 visit per week, 30 minutes long	
In-Clinic Activities	Progressive immersive training with the C.S.I. app	Progressive gait, gaze stability and balance exercises
Program Guidelines	Scenes: start from most salient to the patient, eventually do all Duration: start at 60 seconds, increase over time up to 3 minutes per scene Complexity: start minimal, gradually increase up to most complex Tasks: standing with diverse base of support (BOS), head turns (progress with speed, planes); stepping, turning	Gait: walking with head turns, progress with range, speed and planes of head movement; change of walking BOS: wide, normal, tandem Gaze: focus on a target while moving head side to side / up down. Progress with speed, duration, busier background, standing to walking. Balance: standing balance tasks, progress with BOS (wide to narrow to tandem), support surface, eyes closed, duration, head turns.
Progression / Regression Rule	The highest level of challenge that can be done for 60 seconds with no loss of balance (LOB); No more than moderate symptoms in clinic based on the Simulator Sickness Questionnaire  ; If symptoms persisted over 2 hours post-session, we will scale back the next time. If symptoms improved immediately, we will repeat the task with the same intensity and duration.	
Home Dose	8 weeks, 6 times per week, twice per day, 10 minutes long	
In-Home Activities	Gait and balance exercises, No exercises with eyes closed	Gait, gaze stability and balance exercises, including exercises with eyes closed
Home Prescription	Highest level of challenge that is safe (no LOB, no increased symptoms) for 60 seconds per task

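### The only post-assessment is timed from session 8, so as written the intent-to-treat comparison of VVAS and FGA has no observed outcomes from patients who stop early

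*Protocol*

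**What the plan says.** Two sections of the protocol time the post-assessment, and both time it from the sessions. Procedure says "the patients were randomized to 8 sessions of either traditional vestibular rehabilitation or C.S.I training followed by an immediate post assessment". Interventions says "We conducted a post-assessment, identical to the baseline assessment, within one week from the completion of the" eighth session. The intended length is given there too: "We planned each program to be 8 weeks", with one session a week. Neither section gives a visit or a time window for a randomized patient who attends fewer than eight sessions, and nothing else in the supplied text does.

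The SAP (Data Analysis, Aim 3) sets the analysis: "following the intent-to-treat principle, a linear regression model will be fit with the VVAS and FGA as the primary dependent variable", adjusted for pre-test scores and other baseline covariates. For gaps it says "we will fit a pattern mixture model to multiply impute any missing values", pooled by Rubin's rules. Aim #2 lists the attrition rate among the things the pilot should establish, so some loss is expected. The use of the result is explicit: "The current study will allow us to identify the between-group effect size for the VVAS and for a functional gait outcome" (Aim #3), and "Data generated from this pilot randomized trial will be used to calculate the sample size needed for future, adequately powered, randomized controlled trials" (Data Analysis, Aim 3).

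**The concern.** An intent-to-treat estimate differs from a completers' estimate only through the patients who do not complete. A schedule that starts the outcome visit at completion of session 8 collects nothing from them. Their VVAS and FGA would all be imputed, and the data would say nothing about how far they differ from completers.

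This matters if stoppers differ from completers by different amounts in the two arms, or if the arms stop at different rates. Neither can be ruled out. The in-clinic programs differ (immersive app against conventional exercises), and progression in both is guided by symptoms. The documents do not show that stopping does differ by arm. If it does, the between-group difference passed to the next trial's sample-size calculation depends on an assumed shift. The error can go in either direction.

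**Working it through.** **Figures in the documents.** There is none to reproduce. The documents state no sample size, attrition, outcome SD or between-group effect. The 1.17 in SAP Aim #3 is the effect seen in 8 patients following C.S.I. training, not a difference between arms. Everything below is an illustration on assumed inputs.

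**Assumed inputs.** 20 patients per arm, outcome SD 1, baseline correlation 0.6, and a completer difference of 0.50 SD. Let p be the proportion stopping, s how much worse stoppers do (in SD), and r the share of stoppers recalled for assessment. T is C.S.I. and C is control.

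**Formulas.**
- Effect in all randomized patients: 0.50 − pT·sT + pC·sC.
- Expected estimate from assessed patients, random recall: 0.50 − sT·pT·r/(1 − pT + pT·r) + sC·pC·r/(1 − pC + pC·r).

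**Base case: pT = pC = 0.20, sT = 0.50, sC = 0.** The true effect is 0.50 − 0.20 × 0.50 = 0.40. At half recall the formula gives 0.50 − 0.50 × 0.10/0.90 = 0.444. A simulation (40,000 runs, regression on arm and baseline among assessed patients) gave:

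| Stoppers recalled | Mean | Bias | SD | RMSE |
|---|---|---|---|---|
| None | 0.500 | 0.10 | 0.290 | 0.307 |
| 25% | 0.471 | 0.07 | 0.282 | 0.291 |
| 50% | 0.444 | 0.04 | 0.274 | 0.278 |
| 75% | 0.421 | 0.02 | 0.267 | 0.268 |
| All | 0.400 | 0.00 | 0.260 | 0.260 |

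An independent 20,000-run repeat gave RMSE 0.306, 0.277 and 0.259 for none, half and all recalled.

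**Variations.**
- Stopping rate, same shift: RMSE for none against all recalled is 0.277 against 0.259 at 10% per arm, and 0.347 against 0.261 at 30%.
- Trial size at 20% stopping: 0.398 against 0.341 with 24 patients, and 0.255 against 0.212 with 60.
- Equal dropout (20%) and equal shift (0.50): true effect 0.50 and bias at most 0.004 throughout. Full recall only improves precision (SD 0.290 to 0.264).
- Unequal dropout (10% C.S.I., 30% control), both shifts 0.50: true effect 0.50 − 0.05 + 0.15 = 0.60. The mean is 0.498 with none recalled, 0.560 with half and 0.598 with all. Here the completers' estimate is too small.
- Selective recall in the base case, with only the better-scoring half of C.S.I. stoppers returning: bias 0.115 and RMSE 0.291, against 0.10 and 0.307 with none recalled.

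**Dependence on the assumed shift.** A 0.50 SD shift applied in one arm to patients still unassessed moves the estimate by p·(1 − r)·0.50. That is 0.20 × 1 × 0.50 = 0.10 with none recalled, 0.20 × 0.50 × 0.50 = 0.05 with half, and 0.20 × 0.25 × 0.50 = 0.025 with 75%.

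**Scale for the next trial.** For a two-sample t-test at two-sided 5% and 80% power (both assumed), 0.50 SD needs 64 per arm and 0.40 SD needs 100.

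**The case against.** The protocol is silent on early stoppers; it does not refuse them assessment. Interventions is a short account in the past tense that gives the usual timing for someone who follows the program, and the SAP's intent-to-treat principle is compatible with assessing stoppers. Some pages were not available, and the SAP's imputation sentence points back to a description that is not in the supplied text. All of this stands. The claim is therefore limited to what happens if the schedule is followed as written, and no complaint is made about the detail of the imputation model.

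Missing data are addressed, and the bias and RMSE figures come from a regression on assessed patients, not from the planned analysis. This also stands. In a simplified check with nobody recalled (12,000 runs, not a full imputation), subtracting the correct 0.50 SD for unassessed C.S.I. patients gave a mean of 0.403 and RMSE 0.292. Subtracting half of it gave 0.449 and 0.295. So 0.10 SD is not the expected bias of the planned analysis. But the correction works only as well as the shift is guessed, and the schedule collects nothing to inform the guess.

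Much of the gain is precision: in the base case, SD alone falls by 0.030 of the 0.047 drop in RMSE. Selective return can leave the bias no better. A pilot with a standard error near 0.3 SD cannot tell 0.50 from 0.40. These are fair limits on the size of the benefit, but they do not favor leaving stoppers unassessed: RMSE fell with recall even in the selective case.

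Finally, visits may already be complete. The remedy then reduces to reporting and sensitivity analysis.

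**Conclusion.** The concern holds on the supplied text. Procedure and Interventions agree in timing the single post-baseline assessment from the eight sessions, and no visit is given for a patient who stops before then. If that was followed, the intent-to-treat comparison of VVAS and FGA has no observed stoppers, and the pattern mixture model has to assume how they differ.

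Under the unfavorable base case, an analysis of assessed patients is off by 0.10 SD, about a third of the pilot's sampling error. The error can reverse sign, and it is zero when dropout and shift are the same in both arms. All of these sizes rest on assumed sample size, attrition, shift and correlation. This is a worthwhile and inexpensive improvement, not a fatal flaw. Confidence is medium, because the documents do not show whether any stopper was in fact assessed.

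**What to change.** In the protocol, state that the post-assessment, at minimum VVAS and FGA, is attempted in every randomized patient who has not withdrawn consent, however many sessions were attended. Keep the session-8 timing for those still attending. For those who stop, use a calendar window from randomization, about the week after the planned 8 weeks. Record the actual time from randomization for everyone.

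In the SAP, state that the Aim 3 regression includes all assessed patients and that the planned pattern mixture imputation covers those still missing. Add a pre-set range of shifts as a sensitivity analysis. Reporting attrition by arm with exact 95% intervals under Aim 2 would be a useful but optional addition.

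If visits are already complete, report by arm how many patients were not assessed and how many sessions they attended, and rely on the shift sensitivity analysis.

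The cost is a sentence or so in each document, the effort of recalling stoppers, and some variation in assessment timing. On the burden of the full assessment, Procedure says "The total duration of the session was approximately 45 minutes"; limiting recall to VVAS and FGA would shorten that. The benefit depends on how many stoppers return and whether they resemble those who do not.
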